1.4.2 Experience in Pemphigus Patients in Study PRN1008-005

1.4.2.1 Efficacy

As of January 18, 2018, PRN1008 had been administered to 21 patients with pemphigus (pemphigus vulgaris [PV] and pemphigus foliaceus [PF]), 18 of whom had 4 or more weeks of treatment. Of the 18 patients with efficacy data, 11 (61%) met the primary endpoint of “Control of Disease Activity” (CDA) on a CS dose of ≤ 0.5 mg/kg/day (low-dose CS) by the Week 5 visit. Three patients achieved CDA on no CS (Figure 2). Two patients required high-dose CS temporarily during PRN1008 treatment due to worsening of disease activity. Four patients achieved complete remission (CR) on 1 to 20 mg/day of CS; 3 achieved CR at Week 13 (25%) and one achieved CR at Week 21. Responses were seen in patients with both mild and moderate levels of initial disease (PDAI patient profiles, Figure 3).

Figure 2 PDAI and Clinical Response Patient Profiles of 5 Patients on Zero or Doses of CS ≤ 5 mg

[figure not shown]
[figure not shown]

Figure 3 Timing of Individual Clinical Responses (Day 15 to 29 circled) N=21

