APPENDIX 1A CORTICOSTEROID RESCUE CRITERIA AND TREATMENT PROTOCOL (PART A)

Systemic corticosteroids will be avoided during PRN1008 monotherapy unless these rescue criteria are triggered, as described below, or if patients enter the study on low doses (≤ 0.5 mg/kg mg per day). In each rescue scenario, the recommended method of corticosteroid taper is shown in [Appendix 7](#).

Rescue Criteria #1: Flare which, in the mind of investigator, is potentially life threatening

- Commence conventional immunosuppressive therapy and discontinue PRN1008

Rescue Criteria #2: Development of severe but not life-threatening PV (defined as PDAI score ≥ 45) at any time during PRN1008 therapy:

- If most recent BTK trough occupancy was 50% or more, commence conventional immunosuppressive therapy and discontinue PRN1008
- If most recent BTK trough occupancy was $< 50\%$ and PRN1008 dose has not been increased since last BTK assay, commence, or increase dose to, full-dose prednis(ol)one (1.0 mg/kg) orally and increase dose of PRN1008 by an amount agreed to with the Sponsor's Medical Monitor. At next review:
 - If not responding, commence conventional immunosuppressive therapy and discontinue PRN1008
 - If responding, maintain or taper corticosteroids as clinically appropriate while maintaining PRN1008 treatment
- If no BTK trough occupancy is available to guide therapy, maintain PRN1008, and commence, or increase to, full-dose prednis(ol)one (1.0 mg/kg) orally. Seek to expedite latest BTK trough occupancy test result or arrange for a new blood draw to measure BTK trough occupancy. At next review:
 - If not responding, commence conventional immunosuppressive therapy and discontinue PRN1008
 - If responding, maintain or taper corticosteroids as clinically appropriate while maintaining PRN1008 treatment (including adjust dose upwards if BTK trough occupancy $< 50\%$ in consultation with the Sponsor Medical Monitor)

Rescue Criteria #3: Patients with non-severe PV but who fail to achieve “Control of Disease Activity (CDA*)” by 4 weeks

- If most recent BTK trough occupancy was 50% or more, commence, or increase dose to, low dose prednis(ol)one (0.5 mg/kg) orally. Review after another ~2 weeks:
 - If not responding, commence conventional immunosuppressive therapy and discontinue PRN1008
 - If responding, maintain or taper corticosteroids as clinically appropriate while maintaining PRN1008 treatment

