3.3. Treatments

PRN1008 Dosage Initial PRN1008 dosing will be 400 mg *bid*. The maximum dose in this study, after dose adjustment, will be 600 mg *bid*. Patients will be treated with PRN1008 for a maximum of 12 weeks. PRN1008 tablets should be taken with a glass of water and may be taken with or without food, i.e., a period of fasting is not required.

Based on available data from clinical studies PRN1008-001 and PRN1008-002, a 400 mg *bid* oral dose of PRN1008 to be used in this study is expected to be safe and well tolerated. The 400 mg *bid* starting dose is also based upon the dose known to produce ~70% BTK occupancy at trough (~85% average occupancy over the day), as adjusted by results of the relative bioavailability study, where the tablet had ~70% of the exposure of the equal dose of the liquid formulation.

Each PRN1008 film-coated tablet contains either 100 mg or 300 mg of PRN1008 drug substance. In addition, the tablet contains Microcrystalline Cellulose (filler), Crospovidone (disintegrant), Sodium Stearyl Fumarate (lubricant) and a non-functional film coating. The 100 mg tablet is a round shape and orange in color. The 300 mg tablet is an oval shape and white in color.

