8.2.6. Time to first CDA, CR, End of Consolidation Phase, and Relapse

Time to first CDA is defined as the following:

$$\text{Time to first CDA} = \text{Date of the first CDA confirmed} - \text{Date of first dose} + 1.$$

Time to first CR and End of Consolidation Phase are defined in the same way as Time to first CDA.

Time to first relapse after PRN1008 treatment completion or discontinuation is defined as the following:

$$\text{Time to first Relapse} = \text{Date of the first relapse after Week 13 visit confirmed} - \text{Date of last PRN1008 dose} + 1.$$

If the date of last PRN1008 dose is missing, the date of the Week 13 visit during treatment will be used. If patients did not complete the Week 13 visit they will be excluded from the relapse analysis.

The time to relapse analysis will be conducted in two subpopulations for each analysis population: 1) Patients with CDA at the Week 13 visit, 2) Patients with CR at the Week 13 visit.

Patients who have not achieved the above events by the date of study completion or discontinuation will be censored at the date of completion or discontinuation respectively.

Kaplan-Meier survival distribution plots for time to each event will be provided. Kaplan-Meier estimates of quartiles in days and its associated 80% and 95% CI will be calculated by using the LOGLOG transformation. Min and Max survival times in days as well as number of the patients and the probability of experiencing the event on or before specific date will be provided in a table.

The CDA status, CR status, End of Consolidation Phase status, and Relapse status by visit, by patient will be presented in a listing.

Duration of CR will be summarized and listed, and is defined by the last known CR date – first known CR date + 1. Each subject will only have one CR date as a result.

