n (%)	xx (xx.x)	xx (xx.x)	xx (xx.x)	xx (xx.x)
80% CONFIDENCE INTERVAL	(xx.x, xx.x)	(xx.x, xx.x)	(xx.x, xx.x)	(xx.x, xx.x)
95% CONFIDENCE INTERVAL	(xx.x, xx.x)	(xx.x, xx.x)	(xx.x, xx.x)	(xx.x, xx.x)
Cumulative Responder Rate by WEEK5 D29				
n (%)	xx (xx.x)	xx (xx.x)	xx (xx.x)	xx (xx.x)
80% CONFIDENCE INTERVAL	(xx.x, xx.x)	(xx.x, xx.x)	(xx.x, xx.x)	(xx.x, xx.x)
95% CONFIDENCE INTERVAL	(xx.x, xx.x)	(xx.x, xx.x)	(xx.x, xx.x)	(xx.x, xx.x)
...				
Cumulative Responder Rate by WEEK25 D169				
n (%)	xx (xx.x)	xx (xx.x)	xx (xx.x)	xx (xx.x)
80% CONFIDENCE INTERVAL	(xx.x, xx.x)	(xx.x, xx.x)	(xx.x, xx.x)	(xx.x, xx.x)
95% CONFIDENCE INTERVAL	(xx.x, xx.x)	(xx.x, xx.x)	(xx.x, xx.x)	(xx.x, xx.x)

Note: Patients are classified into different dose levels according to the maximum dose they received during the 12 week treatment period. Control of disease activity (CDA) is defined as the time at which new lesions cease to form and established lesions begin to heal. Cumulative responder rate is used, i.e., any patient achieves the response at any study visit is counted into all the later study visits. Unscheduled visits are not included in this summary. Patients who ever achieved CDA on or before a specific visit during the study treatment will be counted as responders. Two-sided 80% and 95% confidence intervals are calculated using the Exact (Clopper-Pearson) method. Percentages are based on the number of patients in the respective dose levels in the Analysis Population.
Source Data: Listing 16.2.4.1.5

<DIRECTORY PATH>PROGRAM NAME Executed: DDMMYYYY hh:mm

Repeat above table with other populations:

Table 14.2.2.4.4.2

Cumulative Incidence of Patients who Achieved Control of Disease Activity (CDA) by Visit
mITT Population

Table 14.2.2.4.4.3

Cumulative Incidence of Patients who Achieved Control of Disease Activity (CDA) by Visit
Per Protocol Population

Table 14.2.2.4.5.1

Cumulative Incidence of Patients who Achieved Control of Disease Activity (CDA) without Prednis(ol)one >0.5 mg/kg by Visit
ITT Population

Visit	400 mg (N=xx)	500 mg (N=xx)	600 mg (N=xx)	Total (N=xx)
Cumulative Responder Rate by WEEK3 D15				
n (%)	xx (xx.x)	xx (xx.x)	xx (xx.x)	xx (xx.x)
80% CONFIDENCE INTERVAL	(xx.x, xx.x)	(xx.x, xx.x)	(xx.x, xx.x)	(xx.x, xx.x)
95% CONFIDENCE INTERVAL	(xx.x, xx.x)	(xx.x, xx.x)	(xx.x, xx.x)	(xx.x, xx.x)
Cumulative Responder Rate by WEEK5 D29				
n (%)	xx (xx.x)	xx (xx.x)	xx (xx.x)	xx (xx.x)
80% CONFIDENCE INTERVAL	(xx.x, xx.x)	(xx.x, xx.x)	(xx.x, xx.x)	(xx.x, xx.x)

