141 DAYS	xx.x (xx)	xx.x (xx)	xx.x (xx)	xx.x (xx)
169 DAYS	xx.x (xx)	xx.x (xx)	xx.x (xx)	xx.x (xx)

Note: Patients are classified into different dose levels according to the maximum dose they received during the 12 week treatment period. Control of disease activity (CDA) is defined as the time at which new lesions cease to form and established lesions begin to heal.

[1] Time to first CDA = Date of first CDA confirmed - Date of first dose + 1. Patients who did not achieve CDA by the date of study completion or discontinuation were censored at the date of completion or discontinuation respectively. 80% and 95% confidence intervals are calculated using the LOGLOG transformation.

[2] * indicate that this value is from a censored data.

[3] Kaplan-Meier estimate of the probability of experiencing the event on or before the specified timepoint (n' = number of patients remaining at risk beyond the specified timepoint).

Source Data: Listing 16.2.4.1.6

<DIRECTORY PATH>PROGRAM NAME Executed: DDMMYYYY hh:mm

Repeat the table above with the following population.

Table 14.2.3.1.2

Time to First Control of Disease Activity (CDA): Kaplan Meier Estimates
mITT Population

Table 14.2.3.1.3

Time to First Control of Disease Activity (CDA): Kaplan Meier Estimates
Per Protocol Population

Table 14.2.3.2.1
Time to First Complete Response (CR): Kaplan Meier Estimates
ITT Population

	400 mg (N=xx)	500 mg (N=xx)	600 mg (N=xx)	Total (N=xx)
TIME TO FIRST CR (days) [1]				
n	xx	xx	xx	xx
25% QUARTILE	xx.x	xx.x	xx.x	xx.x
80% CONFIDENCE INTERVAL	(xx.x, xx.x)	(xx.x, xx.x)	(xx.x, xx.x)	(xx.x, xx.x)
95% CONFIDENCE INTERVAL	(xx.x, xx.x)	(xx.x, xx.x)	(xx.x, xx.x)	(xx.x, xx.x)
MEDIAN	xx.x	xx.x	xx.x	xx.x
80% CONFIDENCE INTERVAL	(xx.x, xx.x)	(xx.x, xx.x)	(xx.x, xx.x)	(xx.x, xx.x)
95% CONFIDENCE INTERVAL	(xx.x, xx.x)	(xx.x, xx.x)	(xx.x, xx.x)	(xx.x, xx.x)
75% QUARTILE	xx.x	xx.x	xx.x	xx.x
80% CONFIDENCE INTERVAL	(xx.x, xx.x)	(xx.x, xx.x)	(xx.x, xx.x)	(xx.x, xx.x)
95% CONFIDENCE INTERVAL	(xx.x, xx.x)	(xx.x, xx.x)	(xx.x, xx.x)	(xx.x, xx.x)
MIN, MAX [2]	xx, xx	xx, xx*	xx, xx	xx*, xx
KAPLAN-MEIER ESTIMATE % (n') [3]				
15 DAYS	xx.x (xx)	xx.x (xx)	xx.x (xx)	xx.x (xx)
29 DAYS	xx.x (xx)	xx.x (xx)	xx.x (xx)	xx.x (xx)
57 DAYS	xx.x (xx)	xx.x (xx)	xx.x (xx)	xx.x (xx)
85 DAYS	xx.x (xx)	xx.x (xx)	xx.x (xx)	xx.x (xx)
113 DAYS	xx.x (xx)	xx.x (xx)	xx.x (xx)	xx.x (xx)
141 DAYS	xx.x (xx)	xx.x (xx)	xx.x (xx)	xx.x (xx)
169 DAYS	xx.x (xx)	xx.x (xx)	xx.x (xx)	xx.x (xx)

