5.4.2.2 Time-to-Event

The following time-to-event analyses will be performed by dose level and overall for events occurred after date of first study drug dosing:

- a) Time to first CDA
- b) Time to first CR
- c) Time to first ECP
- d) Time to first relapse (after CDA has been achieved, as per the definition of relapse) after first dose of study drug
- e) Time to first increase in PDAI

For each event listed above, the number of days to the event will be calculated as:

(Date of first occurrence of event – Date of first study drug dosing of the dose level where the event is observed) + 1

The number of days to first occurrence of each event (a to d) will be summarized by descriptive statistics for each dose level and overall.

Patients who did not achieve the specific event are censored at the last day in a dose level or date of study completion/discontinuation.

Kaplan-Meier estimates of quartiles in days and their associated 80% and 95% CI will be calculated by using the LOGLOG transformation. Minimum and maximum survival times in days as well as number of the patients and the probability of experiencing the event on or before specific date will be provided in a table.

A sensitivity analysis using the Completer and PP populations will be provided.

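### Part A Kaplan-Meier tables for first CDA, CR and end of consolidation censor efficacy failures and count off-drug or post-rescue responses, so they sit at or above the proportion responding on PRN1008

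*SAP*

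**What the plan says.** **Event and censoring.** Part A SAP 8.2.6 measures time to first CDA from the first dose to the first confirmed CDA, and adds: "Time to first CR and End of Consolidation Phase are defined in the same way as Time to first CDA". The censoring rule is: "Patients who have not achieved the above events by the date of study completion or discontinuation will be censored at the date of completion" or of discontinuation. Neither rule depends on whether the patient is still taking PRN1008 or has started rescue. The shell for Table 14.2.3.1.1 reports the "Kaplan-Meier estimate of the probability of experiencing the event on or before the specified timepoint", with rows at 15, 29, 57, 85, 113, 141 and 169 days. The CR and ECP shells have the same rows.

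**Treatment period.** SAP 3.3: "Patients will be treated with PRN1008 for a maximum of 12 weeks". SAP 3.1 adds 12 weeks of follow-up, so the last three rows fall after treatment.

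**Rescue and exit.** For the most serious flare, Protocol Appendix 1A says: "Commence conventional immunosuppressive therapy and discontinue PRN1008". Branches of the other two rescue criteria lead to the same step, while some keep PRN1008 and add prednis(ol)one. SAP 5.1 lists lack of efficacy and progressive disease among the withdrawal reasons.

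**Other rules in the same SAP.** Section 3.2.3 allows CR only on 10 mg/day of prednisolone or less. Sections 8.1 to 8.2.3 classify unknown status as non-response. Section 8.2.5 keeps a fixed denominator for cumulative incidence. A footnote to Table 14.2.2.4.4.1 reads "Patients who ever achieved CDA on or before a specific visit during the study treatment will be counted as responders", yet its rows run to Week 25.

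**The concern.** Kaplan-Meier censoring assumes that a censored patient has the same later chance of response as those still followed. That is implausible for someone who leaves because the drug failed. Separately, a patient who stops PRN1008 but stays in the study remains at risk, and a CDA reached on conventional therapy becomes an event on the same curve as responses to PRN1008.

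The two routes act on different patients: leavers are censored, stayers can add events. Both push the curve up relative to the proportion responding on drug. With a single arm, no control group absorbs the effect of rescue, and SAP 4.1 says that the results will be used to design confirmatory trials. A reader who took the Day 85 or Day 169 figure as the chance of responding to PRN1008 would plan on too high a rate.

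**Working it through.** **1. The plan's own figure.** SAP 4.1 gives an 80% interval of ±13% for a 50% response in 25 patients. Check: 1.2816 × √(0.5 × 0.5 / 25) = 0.128, so it reproduces. No figure is given for the time-to-event analyses.

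**2. Direction.** Let S be the product-limit estimate. With censoring before the time point, 1 − S(t) is never below (observed events by t) / N, and observed events are never fewer than on-drug events. Equality with the on-drug proportion needs two things: no failure leaves before responding, and no first response comes after PRN1008 stops or rescue starts. This follows from the rules alone.

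**3. CDA illustration (all counts assumed).** N = 25. First CDA: 5 at Day 15, 6 at Day 29, 2 at Day 57 and 1 at Day 85, all on drug. The on-drug proportion is 14/25 = 56.0%. Let f further patients leave the study for failure at Day 43.

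- S(29) = 14/25.
- S(57) = S(29) × (12 − f)/(14 − f).
- S(85) = S(57) × (11 − f)/(12 − f) = (14/25) × (11 − f)/(14 − f).

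If one other patient stops PRN1008, is rescued, stays in the study and reaches CDA at Day 85, the last factor becomes (10 − f)/(12 − f), so S(85) = (14/25) × (10 − f)/(14 − f).

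| f | 1 − S(85), no post-rescue CDA | Excess over 56.0% (points) | 1 − S(85), one post-rescue CDA | Excess (points) |
|---|---|---|---|---|
| 0 | 56.0% | 0 | 60.0% | 4.0 |
| 2 | 58.0% | 2.0 | 62.7% | 6.7 |
| 4 | 60.8% | 4.8 | 66.4% | 10.4 |
| 6 | 65.0% | 9.0 | 72.0% | 16.0 |
| 8 | 72.0% | 16.0 | 81.3% | 25.3 |

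The fixed-denominator table under 8.2.5 would show 14/25 = 56% without the rescued responder. With that patient counted it would show 15/25 = 60%. The two sets of tables can therefore disagree on the same data.

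**4. CR illustration (assumed, N = 25).** Three CRs at Day 85 on treatment give 3/25 = 12.0%. Add one CR at Day 141, and f exits at Day 43. Then 1 − S(169) = 4/(25 − f). For f = 0, 2, 4, 6 and 8 this is 16.0%, 17.4%, 19.0%, 21.1% and 23.5%, an excess of 4 to 11.5 points.

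**5. Off-drug responses occur.** Protocol 1.4.2.1 reports, at the January 2018 cut, that "3 achieved CR at Week 13 (25%) and one achieved CR at Week 21". Under the 12-week design then in force, the Week 21 visit (Day 141) is 141 − 85 = 56 days, or 8 weeks, after the Week 13 visit.

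**6. Effect of the remedy.** In step 3 without the rescued responder, the Aalen-Johansen estimate with exit as a competing event adds 5/25 + 6/25 + 2/25 + 1/25 = 14/25 = 56.0% for every f.

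**The case against.** **The estimand is assumed.** Protocol 11.2 lists time to CDA and time to CR with no on-treatment limit, while neighbouring endpoints carry time and steroid limits. The tables may simply describe time to first response under whatever care followed. This stands in part: the excess is relative to an on-drug reading, and no estimand is stated. If rescue is part of the strategy, counting later responses is coherent. Equal prospects for patients who left through failure would still need justification, though the direction of that error would then be unknown.

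**Much is already covered.** Section 8.2.5 does not censor, and its tables are split by prednis(ol)one above 0.5 mg/kg. This stands: step 6 shows that the competing-event estimate can coincide with the fixed-denominator proportion. What 8.2.5 does not separate is response on non-steroid rescue or after the last dose, and it does not correct the Kaplan-Meier probabilities and quartiles.

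**Stronger readings that the documents do not support.**

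- A reader might infer that a CR on 1.0 mg/kg prednisolone counts. It does not at ordinary adult weights: the 10 mg/day limit in 3.2.3 excludes it, leaving only CR after taper or off drug.
- A reader might take the Week 21 CR as a rescue response. Nothing says so. It shows only that responses occur after the planned course. The protocol gives steroid doses of 1 to 20 mg/day across its four CRs, so whether this one meets the SAP limit is not known.
- A reader might apply both routes to the same patients. A patient who stops PRN1008 but stays in the study is not censored and, without a response, does not inflate the curve.
- A reader might call the 29-day row wrong because Week 5 visits may fall up to Day 32. The row is correct as labelled.
- A reader might carry the point to Part B. Its section 5.4.2.2 has a different rule, "Patients who did not achieve the specific event are censored at the last day in a dose level or date of study completion/discontinuation", and planned treatment there runs to Day 169.

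**Conclusion.** The point holds for Part A 8.2.6. The Kaplan-Meier probability of first CDA, CR or ECP is at or above the proportion responding on PRN1008, and it can exceed the SAP's own cumulative incidence. The rescue route matters mainly for CDA and ECP; for CR the remaining routes are response after taper or after PRN1008 has ended.

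The direction rests on reading the censoring date as leaving the study, which fits rows that continue to Day 169. The size is not known. Under the assumed counts the CDA excess at Day 85 is 0 to 16 points from censoring alone, and 4 to 25 points with one post-rescue responder. The upper end of the first range exceeds the planned 80% half-width of about 13 points, but it needs 8 of 25 patients to leave for failure, for which there is no documentary basis. The only related figure is two patients, among 21 treated, who needed high-dose steroid temporarily while on PRN1008.

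A reader might conclude that the trial's main result is compromised. It is not: the primary endpoint counts unknown Week 5 status as non-response, and these are secondary, descriptive tables in a pilot study. The change is worthwhile because it is cheap, not because the analysis fails without it.

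**What to change.** In Part A SAP 8.2.6 and the matching table and figure footnotes:

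1. For CDA, CR and ECP, treat study exit for lack of efficacy, progression or rescue as a competing event (Aalen-Johansen), or keep these patients as non-responders to the end of follow-up. Keep censoring for exits unrelated to efficacy.
2. Flag any first CDA, CR or ECP dated after the last PRN1008 dose, or after the start of conventional immunosuppressive rescue, and tabulate these separately. Give the on-drug, pre-rescue estimate beside the all-response estimate, and state which question each answers.
3. Correct the footnote on the cumulative CDA and CR tables so that it agrees with rows running to Week 25.

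Leave the 8.2.5 denominator and the nominal-day rows as they are. Assess Part B 5.4.2.2 separately under its own dose-level censoring rule.

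The cost is SAP wording and some reprogramming. Dose dates, response dates, medication records and withdrawal reasons are already collected. The reported probabilities may come out somewhat less favourable.
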